13.0 CRITERIA FOR REMOVAL FROM STUDY

Participants will be removed from the protocol for any of the following reasons:

- Development of disease progression that warrants a change in the radiation or chemotherapy treatment plan or an alternative therapy.
- Any grade 4 non-hematologic toxicity, except in cases where the treating physician believes the patient is deriving benefit from remaining on the study.
- Chemotherapy treatment delay of 3 consecutive weeks for any reason
Note: Disruption to the cisplatin treatment schedule for 3 weeks due to unforeseen circumstances, holidays or the patient being on vacation is permitted and will be reviewed on a case-by-case basis.
- For safety reasons, the investigator considers it to be in the best interest of the participant that they be withdrawn
- The patient wishes to withdraw from the study
- HRR status is unable to be obtained from the core biopsy taken at the beginning of the study.

14.0 BIOSTATISTICS

The proposed study is a prospective Phase II trial testing the efficacy of concurrent cisplatin and radiation in TNBC patients with measurable metastatic or locally recurrent tumor, based on HRR status. All patients (regardless of HRR status) who meet the eligibility criteria and agree to be part of the trial will be enrolled. That is, knowledge of HRR status is not necessary at the start of the study, as all patients will receive the study therapy of concurrent cisplatin and radiation. The primary objective of this trial is to evaluate whether patients with HRR-deficiency have higher *complete response* (CR) rates than patients who are HRR-proficient. For the primary endpoint, response will be measured at 12+- 2 weeks after the completion of RT.

Preliminary data from our institution has demonstrated the incidence of HRR deficiency in non-metastatic TNBC patients to be 48% [13]. However, because these studies were performed in non-metastatic breast cancer patients and cannot be fully extrapolated to metastatic patients, we conservatively estimated that the incidence of HRR deficiency in our proposed study population of patients with locally recurrent or metastatic TNBC to be 40%. Based on preliminary data from Washington University in which HRR-deficient patients had a greater than 4-fold pathologic CR rate compared to HRR-proficient patients [39], we conservatively assumed that HRR-deficient patients would achieve approximately 2.5x higher CR rate than HRR-proficient patients. We estimated that the CR rate of in HRR-proficient patients following concurrent cisplatin and RT to be 30%, and that the CR rate in HRR-deficient patients would be increased to 65%. This corresponds to an absolute difference in CR rates of 35%. These estimates were based on response rates after platinum

chemotherapy observed in metastatic TNBC patients in the TBCRC009 study [39] and adjusted for the additional cytotoxic effect of radiation therapy on the target tumor. The below table provides power calculations for varying proportions of HRR deficiency (30% to 40%), assuming a one-sided type I error of 5% and for a sample size of **54**.

Proportions of estimated HRR-deficiency	Power for absolute CR difference of 35%, n=54 Power Calculations
40%	85%
35%	83%
30%	80%

However, we will plan to accrue a total of **62** patients in order to allow for early dropout due to disease progression/death prior to response evaluation, or inability to obtain HRR status from the core biopsy. For the primary analysis, all patients for whom HRR status can be ascertained will be included in the denominator. Patients who progress or die prior to the response evaluation at 12 +/- 2 weeks post-RT will be included as failures. This includes patients with disease progression outside of the irradiated tumor. Patients for whom HRR status cannot be ascertained or who left the study for nondisease related reasons will be replaced.

A secondary analysis of interest is to evaluate the CR rate among the subset of patients who are able to complete the planned study treatment and have a scan at the 12 +/- 2 week post-RT time point. Radiographic complete response (CR) of the irradiated tumor will be counted as a positive response to treatment. Radiographic response less than a CR, progression of the irradiated tumor or appearance of a new lesion within the radiated field will be categorized as a failure to respond to treatment. All other sites of metastatic disease that is outside of the irradiated field will be monitored and counted toward disease progression.

Based on prior experience with the HRR assay, we estimate that approximately 10% of patients will either 1) not have a definitive HRR status, or 2) will not complete the planned study treatment or 3) not have a response assessment at 12-14 week time point. To ensure we have 80% power for both the primary and secondary analyses we have added 8 patients to the sample size for a total of 62. The accrual number has been adjusted to 54 patients.

We expect to accrue 1 to 2 patients per month, or approximately 18 patients per year. Thus, accrual for the trial will be completed in 3.5 years. Based on previous data on the tolerability of cisplatin and radiation extrapolated from head and neck and gynecologic malignancies, we do not anticipate toxicities associated with the study treatment and as such, we have not incorporated an early stopping rule.

Secondary endpoints include overall response rates (CR+PR+stable disease), time to progression and CTCAE v4.0 toxicities. These endpoints will be compared by HRR status using the log-rank test for time-to-event endpoints and Fisher's exact test for binary endpoints.

Exploratory objectives are to evaluate the association of tumor-infiltrating lymphocytes (TIL), other immune correlates within the tumor biopsy specimen and circulating tumor DNA as stated in section 3.6 and 5.4 as a predictor of treatment response. This will be done using a Wilcoxon rank-sum test. In a second exploratory objective, in patients who have both RECIST 1.1 and PRC assessments, agreement will be calculated and if there is a sufficient sample size, a McNemar's test will be done.

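### Section 14 names no test for the primary comparison of CR by HRR status, and its 85/83/80% power table is an approximation that no test holding a one-sided 5% level attains at 54 patients

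*Combined protocol and SAP*

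**What the plan says.** Section 14.0 of the combined protocol and SAP states the primary aim: "The primary objective of this trial is to evaluate whether patients with HRR-deficiency have higher" CR rates than HRR-proficient patients, with response read at 12 ± 2 weeks after RT. It assumes CR rates of 30% (proficient) and 65% (deficient). It then says: "The below table provides power calculations for varying proportions of HRR deficiency (30% to 40%), assuming a one-sided type I error of 5" per cent and a sample size of 54. The power is given as 85%, 83% and 80% for HRR-deficiency of 40%, 35% and 30%. No method is given for that calculation.

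Tests are named only for other purposes. The text lists "Secondary endpoints include overall response rates (CR+PR+stable disease), time to progression and CTCAE v4.0 toxicities", and the next sentence says "These endpoints will be compared by HRR status using the log-rank test for time-to-event endpoints and Fisher's exact test for binary endpoints". The exploratory aims get a Wilcoxon rank-sum test and, for RECIST 1.1 against PRC, "agreement will be calculated and if there is a sufficient sample size, a McNemar's test will be done". No other section names a test for the primary endpoint. The one-sided 5% level appears only as an assumption of the power table.

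On the target, Section 14.0 says "To ensure we have 80% power for both the primary and secondary analyses we have added 8 patients to the sample size", and then "The accrual number has been adjusted to 54 patients".

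**The concern.** The plan specifies tests for its secondary and exploratory endpoints but not for its primary one. With roughly 16 to 22 HRR-deficient patients, the usual tests for two proportions differ enough for the choice to matter. At the design rates, Fisher's test and the pooled z test would reach opposite verdicts in about 8.3/8.6/11.9% of trials at the three splits. An illustrative table, picked because it lies near the boundary, is 14/22 (64%) against 12/32 (38%). Its one-sided p is 0.053 by Fisher, 0.034 by Boschloo and 0.029 by pooled z.

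Section 5.3 says HRR results go to the study statistician and primary investigator while the study runs. A choice of test made at analysis could therefore not be shown to be independent of the data. The stated power also cannot be taken at face value until the test is known.

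**Working it through.** **Inputs, all from Section 14.0.** CR 65% against 30%; one-sided alpha 0.05 (critical value 1.645); N = 54; deficient share 40/35/30%. Exact calculations use whole patients: 22/32, 19/35 and 16/38.

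**Step 1: reproduce the table.** Unpooled approximation: power = Φ(0.35 / √(0.65×0.35/n1 + 0.30×0.70/n2) − 1.645), with n1 = 54 × share and n2 = 54 − n1.

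- 40%: n1 = 21.6, n2 = 32.4. Variance 0.01053 + 0.00648 = 0.01701, SE 0.1304. 0.35/0.1304 = 2.683. Φ(1.038) = 85.0%.
- 35%: n1 = 18.9, n2 = 35.1. Variance 0.01204 + 0.00598 = 0.01802, SE 0.1342. 0.35/0.1342 = 2.607. Φ(0.962) = 83.2%.
- 30%: n1 = 16.2, n2 = 37.8. Variance 0.01404 + 0.00556 = 0.01960, SE 0.1400. 0.35/0.1400 = 2.500. Φ(0.855) = 80.4%.

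These match the stated 85/83/80%. Other forms do not match every row: pooled variance gives 82.8/81.1/78.5%, continuity-corrected 74.2/71.8/68.2%, and two-sided unpooled 76.5/74.1/70.5%.

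**Step 2: exact power and size.** Power is the sum, over all x = 0..n1 and y = 0..n2 that the test rejects, of Bin(x; n1, 0.65) × Bin(y; n2, 0.30). Size is the same sum with one common CR rate in both groups. The rejection rules are:

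- Fisher: hypergeometric upper tail of x given x + y is at most 0.05.
- Boschloo: Fisher's p is the statistic, and its tail probability, maximised over the common CR rate, is at most 0.05.
- Pooled z: (x/n1 − y/n2) / √(p̄(1−p̄)(1/n1+1/n2)) ≥ 1.645, where p̄ = (x+y)/54.
- Unpooled z: the same numerator over the unpooled standard error.

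**Step 3: ceiling for any valid test.** Let each outcome (x, y) have a rejection probability between 0 and 1. Maximise power by linear programming, subject to size at most 5% at a grid of common CR rates. No test of true size 5% can exceed the result.

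| | 40% (22/32) | 35% (19/35) | 30% (16/38) | Maximum size |
|---|---|---|---|---|
| Plan's table | 85 | 83 | 80 | – |
| Ceiling at true size 5% | 82.8 | 80.9 | 77.8 | 5 |
| Boschloo | 82 | 79.6 | 76.0 | 4.9/5.0/4.9 |
| Pooled z | 83.4 | 81.4 | 79.6 | 5.7/5.2/6.0 (CR 25–65%) |
| Unpooled z | 84.3 | 83.0 | 79.7 | 6.0/6.7/7.9 (CR 25–65%) |
| Fisher | 75.0 | 72.8 | 67.6 | 2.9/2.9/2.8 |

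All entries are percentages. The plan's figures exceed the ceiling by 85 − 82.8 = 2.2, 83 − 80.9 = 2.1 and 80 − 77.8 = 2.2 points. Fisher would fall 10.0, 10.2 and 12.4 points below the table.

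**Step 4: sensitivity to the split.** At 17/37, Fisher's power is 70.2%. Averaged over a binomial split at 40/35/30% prevalence, power is 80.9/79.0/76.0% for Boschloo, 81.9/80.3/77.8% for pooled z and about 74/72/68% for Fisher.

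**The case against.** A reader might infer that the trial will be analysed with Fisher's test and so has only 68–75% power. The documents do not say that. Fisher is attached to the secondary endpoints, and carrying it over to CR is a plausible default but not a commitment. A reader might also infer that the table is miscalculated. It is not: it follows from the plan's inputs by a recognised large-sample formula, and a pooled z (uncorrected chi-square) test comes within 2 points of every row.

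The inputs are also rougher than the gap. The prevalence rests partly on 6 of 13 TNBCs (Section 3.3.4). As an assumed variation, replacing 65% by 60% in the plan's own formula at 40% prevalence gives Φ(0.30/√(0.24/21.6 + 0.21/32.4) − 1.645) = Φ(0.617), about 73%. Disagreement between tests depends on the split too: Fisher and pooled z differ in 7.0% of trials at 21/33 and 8.8% at 17/37, against 11.9% at 16/38.

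Much of this stands. It limits the power complaint to a few points unless Fisher is used, and it makes the omission the main issue. It does not remove it. Uncertain inputs are no reason to leave the primary test open, and either likely reading calls for an edit: with Fisher the table is 10–12 points too high, and with a z test the size above 5% is undisclosed.

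**Conclusion.** The point holds and should be fixed before analysis. The primary test is unnamed, and the power table states more than any test of true one-sided size 5% can deliver at these splits, by about 2 points. The practical shortfall depends on the test:

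- Boschloo: about 3–4 points.
- Pooled z: under 2 points, with size up to about 6% for CR rates of 25–65%.
- Fisher: 10–12 points, only if it is adopted for the primary endpoint.

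With 79.6% counted consistently as below 80%, Boschloo misses the 80% target in the 35% and 30% rows, and pooled z misses it marginally in the 30% row.

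These figures assume true CR rates of 65% and 30%, the rounded splits shown, and all 54 patients analysed. They do not show that the trial is badly underpowered. The change of accrual from 62 to 54 is a separate matter and is not relied on here.

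**What to change.** Before any analysis by HRR status, add one sentence to Section 14.0 naming the primary test and its one-sided 5% level, and replace the table with that test's exact power at 54 evaluable patients.

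- Preferred: an exact unconditional test such as Boschloo's, with power 82/79.6/76%. It holds its size and has about 7–8 points more power than Fisher.
- Pooled z: state 83.4/81.4/79.6% and a size of up to about 6%.
- Fisher: restate the table as 75/73/68%.
- Unpooled z should not be used, because its size reaches 6.0/6.7/7.9%.

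The edit is one sentence and a three-row table, and standard software covers every option. The price is a less favourable stated power. Keeping at least 80% at 40/35/30% prevalence would need 51/55/59 evaluable patients with Boschloo, 51/53/57 with pooled z and 62/64/71 with Fisher. If accrual stays at 54, the plan should say which rows fall short of the target.

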- If serum creatinine is >1.5 mg/dL, delay treatment, provide intravenous hydration and check 12 or 24 hour creatinine clearance, serum creatinine and electrolytes after 24 hours. If the serum

creatinine is ≤ 1.5 mg/dL and creatinine clearance ≥ 60 cc/min, may give full dose of cisplatin. If serum creatinine is 1.6-1.9 and creatinine clearance is between 30-60 cc/min, cisplatin can be given at the discretion of the treating physician. If serum creatinine is >2 OR creatinine clearance is <30 cc/min, hold cisplatin.

- If the patient develops any non-hematologic grade 3-4 toxicity, cisplatin will be held until toxicity is reduced to grade 2 or less. Dose reduction is permitted at the discretion of the treating physician. If a patient experiences grade 2 toxicity (with exception of alopecia) that lasts >2 weeks, cisplatin will be held and dose reduction recommended at discretion of the treating physician. Cisplatin will be discontinued if greater than grade 2 toxicity persists following 2 dose reductions.
- If the patient develops an intercurrent illness (e.g. infection) that, in the opinion of the treating medical oncologist, mandates a delay of cisplatin therapy, the intercurrent illness must be resolved within a time frame such that no more than 2 weekly doses of cisplatin are withheld. If therapy must be withheld for a longer period of time, the patient will be removed from the study.
- Following the completion of RT but prior to the week 12 post RT evaluable timepoint, patients will continue receiving cisplatin based on MD discretion. The dose and schedule of cisplatin after the completion of RT will be at the discretion of the treating MD. If there is a delay of 3 consecutive weeks of treatment, then the patient must discontinue protocol therapy and will be removed from study. Continuation of cisplatin and the dose and schedule of cisplatin after Week 12 post RT assessment will be at the discretion of the treating MD.
- Note: Disruption to the cisplatin treatment schedule for 3 weeks due to unforeseen circumstances, holidays or the patient being on vacation is permitted and will be reviewed on a case-by-case basis.

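### The secondary completer analysis of CR drops patients the primary analysis counts as failures, yet is given 80% power, so selection alone can shrink or inflate the HRR difference

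*Combined protocol and SAP*

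**What the plan says.** All of the following is in Section 14.0 unless stated.

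- **Primary analysis.** The denominator is every patient whose HRR status can be ascertained. "Patients who progress or die prior to the response evaluation at 12 +/- 2 weeks post-RT will be included as failures", and progression outside the irradiated tumor is included. Patients without an HRR status, or who leave for reasons unrelated to disease, are replaced.
- **Completer analysis.** A secondary analysis looks at "the CR rate among the subset of patients who are able to complete the planned study treatment" and who also have the scan at 12 ± 2 weeks after RT.
- **Power.** The power table is built "assuming a one-sided type I error of 5% and for a sample size of 54", for 65% v 30%, and shows 85%, 83% and 80% at 40%, 35% and 30% HRR deficiency. About 10% of patients are expected to lack an HRR status, not complete treatment, or lack the response assessment. Eight patients were added, making 62, so that both the primary and the secondary analyses have 80% power. The next sentence resets accrual to 54.
- **Treatment after RT.** Section 4.3.1 states: "The dose and schedule of cisplatin after the completion of RT will be at the discretion of the treating MD". Section 14.0 does not say whether this phase belongs to the planned treatment.
- **Removal.** Under Section 13.0, progression that warrants a change of treatment takes the patient off protocol.

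No caveat, table of non-completers by HRR status, or sensitivity analysis is specified for the completer analysis.

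**The concern.** Membership of the completer set is decided after baseline, partly by events that the primary analysis scores as failure. The trial's hypothesis is that the treatment works better in HRR-deficient tumors, so there is reason to expect that the patients removed will not be spread evenly across the two HRR groups. The CR difference among completers can then differ from the primary difference although nothing about the biomarker has changed.

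This would matter little for a purely descriptive summary. The plan instead gives the analysis the same 80% power as the primary. Power has meaning only for a comparison, and the only comparison powered in Section 14.0 is CR by HRR status. At reporting there could be two nominally powered CR results, possibly in disagreement, with no rule for which governs. Because completion is not defined, membership could also be settled after response is known.

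**Working it through.** **Inputs (Section 14.0).** CR 65% (HRR-deficient) v 30% (HRR-proficient); one-sided 5%; N = 54; 40% HRR-deficient; anticipated loss about 10%. Two assumptions are added: all leavers are primary failures, and the split of leavers by HRR status is as shown.

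**1. The plan's own power.** The one-sided z-test with unpooled variance is

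power = Φ(Δ/SE − 1.645), with SE = √[p₁(1−p₁)/n₁ + p₂(1−p₂)/n₂].

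At 40% deficiency, n₁ = 21.6 and n₂ = 32.4. SE = √(0.2275/21.6 + 0.2100/32.4) = 0.130, and Φ(0.35/0.130 − 1.645) = 85.0%. At 35% and 30% it gives 83.2% and 80.4%. All three stated values are reproduced.

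**2. Completer rates at the planned 10% loss.** If a fraction d of a group leaves and all leavers are primary failures, the completer CR rate is p/(1 − d). The overall constraint is 0.4·d₁ + 0.6·d₂ = 0.10.

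| Who leaves | d₁ (deficient) | d₂ (proficient) | Completer CR | Difference |
|---|---|---|---|---|
| All HRR-proficient | 0 | 0.10/0.60 = 16.7% | 65% v 0.30/0.833 = 36% | 29 points |
| Equal loss | 10% | 10% | 0.65/0.90 = 72.2% v 0.30/0.90 = 33.3% | 38.9 points |
| All HRR-deficient | 0.10/0.40 = 25% | 0 | 0.65/0.75 = 86.7% v 30% | 56.7 points |

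In the first row n₂ falls to 27. SE = √(0.2275/21.6 + 0.2304/27) = 0.138, and power = Φ(0.29/0.138 − 1.645), about 68%. With equal loss it is about 90%. Equal loss leaves the ratio of CR rates unchanged (72.2/33.3 = 65/30) but inflates the absolute difference, which is the scale on which the trial is powered.

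**3. Whole patients.** Take a primary result near the planning values: 14/22 v 10/32, difference 32.4 points, one-sided Fisher p = 0.019. Remove five primary failures (about 10% of 54):

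- all five HRR-proficient: 14/22 v 10/27, 26.6 points, p = 0.058;
- two deficient and three proficient: 14/20 v 10/29, 35.5 points, p = 0.015;
- all five HRR-deficient: 14/17 v 10/32, 51.1 points, p = 0.0008.

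With essentially no primary difference (9/22 v 13/32, +0.3 points), five leavers move it to between −7.2 points (9/22 v 13/27) and +12.3 points (9/17 v 13/32).

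**4. The power claim at 54.** This step takes 65% v 30% as the rates among completers. 54 less 10% is about 49 patients, and the step 1 formula gives 81.9%, 79.9% and 76.9% at 40%, 35% and 30% deficiency. The same sum for 62 (about 56 after loss) gives 86.2%, 84.4% and 81.6%. The 80% statement therefore holds across the table at 62 but not at 54.

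**5. Larger losses, as illustration.** Section 3.4 reports that 33% of patients progressed by 6 weeks in the cited platinum-only study in metastatic TNBC. At about that overall loss, exits of 10% v 50% (0.4 × 10% + 0.6 × 50% = 34%) give 72% v 60%, 12 points. An equal 33% gives 97% v 45%, 52 points, though it leaves only 2% of HRR-deficient patients for every other outcome.

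**The case against.** The strongest reply is that the analysis is labelled secondary, the primary handles early progression and death properly, and the HRR groups are not randomised, so no randomised balance is lost. All of this stands. A reader might infer that the primary result is compromised; it is not.

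Other stronger readings also go beyond the documents:

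- **A prescribed test.** The completer sentence names neither an HRR comparison nor a test, and this analysis is not among the endpoints listed for Fisher's exact test. The comparison is inferred from the shared power statement.
- **A fixed direction.** One might infer that more early progression among HRR-proficient patients always dilutes the effect. It does not. Exits of 7% v 12% give 36 points, and 25% v 38% give 38. Dilution needs a large enough imbalance, for example 5% v 13%, which gives 34.
- **A collapse in power.** Exits of 10% v 50% would put power at about 19%. That rests on a loss rate from a study without RT and on an assumed split. At the planned 10%, the least favourable case is about 68%.
- **Post-RT cisplatin as part of completion.** Section 14.0 does not say so. The supportable point is that the term is undefined.

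The arithmetic also simplifies. Patients who stop for toxicity or withdraw need not be primary failures, and those who leave for reasons unrelated to disease are replaced. A scanned patient with local CR and distant progression could be a primary failure yet a completer CR. The 10% also includes missing HRR status, so non-completion alone could be lower. These points affect the size of the shift; they do not remove the conditioning on post-baseline events.

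**Conclusion.** The concern holds for the interpretation and claimed power of the completer analysis, and it should be corrected. At the plan's own 10% loss, a fixed 35-point primary difference becomes anything from 29 to 57 points among completers, and 39 with equal loss. Five patients are enough to move an illustrative result from p = 0.019 to 0.058 or 0.0008. This rests on all leavers being primary failures and on assumed splits by HRR status, for which the documents give no figures. Separately, 80% power is not assured at the current accrual: about 82%, 80% and 77% across the plan's range of HRR deficiency, if the 10% loss comes out of the 54 and is not made good by replacement.

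**What to change.** In Section 14.0:

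1. Withdraw the 80% power claim for the completer analysis, or restate it for 54 patients, and reconcile the 62 and 54 accrual statements.
2. Label the analysis supportive and descriptive, with the analysis of all patients with a known HRR status as the sole basis for inference.
3. Define completion, stating whether discretionary post-RT cisplatin counts toward it.
4. Tabulate non-completers by HRR status and reason.
5. Give best- and worst-case bounds for missing scans.

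Redefining the subset by completion of RT is not a remedy. That milestone is itself post-baseline, and patients who progress or die before it would still be removed.

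The cost is revised wording and one table, with no change to treatment, visits or accrual. The downside is that the sponsor gives up a nominally powered secondary test.

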Finally, the PrECOG 0105 study included 80 TNBC and BRCA1/2 mutated patients treated with neoadjuvant carboplatin, gemcitabine and iniparib [38]. Pathologic CR was achieved in 36% of the overall population, 47% in the BRCA1/2 mutated population and 56% in triple negative patients who also had BRCA 1/2 mutations. The toxicity profile was more favorable than that of the Gepar Sixto regimen, with myelosuppression (grade 3 or 4 neutropenia in 49%) and elevations in liver enzymes (grade 3 in 24%).

Whereas the aforementioned trials evaluated platinum chemotherapy in the neoadjuvant setting, the efficacy of platinum chemotherapy has also been studied in metastatic TNBC patients. TBCRC 009 was a multicenter single-arm phase I study of single-agent platinum in 86 patients with metastatic TNBC [39]. Patients received cisplatin 75mg/m² or carboplatin AUC=6 every 3 wks, by physician choice. The objective response rate (ORR) was 30.2% overall, including 4 CR (4.7%), 22 PR (25.6%). The ORR was 54.5% vs. 19.7% in BRCA1/2 carriers (n=11) vs. non-carriers (n=66); ($p=0.02$). Six long-term responders remain disease-free at median follow up of 4 yrs, 3 of whom stopped treatment after 6 cycles. Exploratory subgroup analysis of RR: Cisplatin 37%, Carboplatin 23%; 1st line therapy 31.7%, 2nd line therapy 20%. 33% of pts progressed by 6 weeks, but 33% remained on study for ≥ 6 mos. 51 treatment-related grade 3/4 toxicities occurred. 2 patients had grade 4 toxicities (neutropenia (1) and hypertension (1)), while the others were grade 3 (fatigue (8), neutropenia (6), anemia (5), hyponatremia (4)).

In a subsequent analysis presented at the ASCO 2014 Annual Meeting, predictors of response to platinum chemotherapy were assessed, including p63/p73 expression by RT-PCR as a predictor of response. Tumor-based exploratory studies included gene expression (GE) profiling, PIK3CA and p53 mutational status, and homologous recombination deficiency (HRD) assays correlating with

BRCA1/2 inactivation. All biomarkers *except* the HRD assays failed to predict responses to platinum chemotherapy. Types of HRD assays performed included Loss of Heterozygosity (LOH), Telomere Allelic Imbalance (tAI), and Large-scale State Transition (LST). Among the small group of 22 patients with available tissue, scores in all of the HRD assays were higher in BRCA1/2 carriers than non-carriers, and in responders than non-responders (HRD-LST responders vs. nonresponders, $p=0.0016$).

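### The 80% power assured for the completer analysis rests on a 10% loss allowance justified only by HRR-assay experience, and it is not secured at the current accrual of 54

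*Combined protocol and SAP*

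**What the plan says.** Section 14.0 (Biostatistics) tabulates power of 85/83/80% at 40/35/30% HRR deficiency for CR rates of 65% (deficient) and 30% (proficient), "assuming a one-sided type I error of 5% and for a sample size of" 54.

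It then describes two analyses. The primary analysis keeps everyone with a known HRR status and counts progression or death before the week-12 scan as failure. A secondary analysis takes only patients who finish treatment and have that scan (the completers).

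For losses, the section says that "we estimate that approximately 10% of patients will either 1) not have a definitive HRR status", and puts non-completion of treatment and absence of the response assessment under the same 10%. The stated basis is past experience with the assay. It continues: "To ensure we have 80% power for both the primary and secondary analyses we have added 8 patients", making 62, and then says that accrual has been adjusted to 54. Patients without an HRR status, and those leaving for reasons unrelated to disease, are to be replaced.

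Two other places bear on the loss rate. Section 3.4, on the single-agent platinum study in 86 patients with metastatic TNBC, reports that "33% of pts progressed by 6 weeks". Section 13.0 lists among the reasons for removal: "Development of disease progression that warrants a change in the radiation or chemotherapy treatment plan or an alternative therapy".

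**The concern.** Assay experience can say how often a biopsy yields no HRR result. It cannot say how often patients with advanced TNBC progress, die or stop treatment before a scan 12 weeks after RT. Section 14.0 itself names progression and death before evaluation as a reason for enlarging the sample, but gives no rate for them. The platinum study that reports 33% progression by 6 weeks is the one Section 14.0 draws on for its CR rates, so it was used for response and not for attrition.

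The eight added patients were the means of securing 80% for the completer comparison. With accrual back at 54 they are gone, but the assurance remains in the text. A reader who trusts it could take a null completer result as stronger evidence against the biomarker than the number of completers allows.

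**Working it through.** **Inputs.** From Section 14.0: p1 = 0.65 (deficient), p2 = 0.30 (proficient), one-sided alpha 0.05 (z = 1.645), share deficient f = 0.40, 0.35 or 0.30, N = 54 or 62, loss 10%. From Section 3.4: 33%. The 20% loss is an assumed intermediate value.

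**1. Reproduce the plan's table.** With n1 = fN and n2 = (1 − f)N,

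power = Φ{ (p1 − p2) / √[p1(1 − p1)/n1 + p2(1 − p2)/n2] − 1.645 }.

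For N = 54 and f = 0.40, n1 = 21.6 and n2 = 32.4. The standard error is √(0.2275/21.6 + 0.21/32.4) = 0.1304, and 0.35/0.1304 = 2.683. Power = Φ(1.038) = 85.0%. The other two rows give 83.2% and 80.4%. All three match the plan. A pooled-variance version gives 82.8/81.1/78.4%, so the unpooled formula is the one that fits.

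**2. Check the allowance.** 54/0.90 = 60, and 62 × 0.90 = 55.8, so 62 patients do cover a 10% loss.

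**3. Completer power, with 65% v 30% applied to completers.** N is replaced by N × (1 − loss):

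| Loss | 54 accrued: completers | Power at f = 40/35/30% | 62 accrued: completers | Power at f = 40/35/30% |
|---|---|---|---|---|
| 10% | 48.6 | 82/80/77% | 55.8 | 86/84/82% |
| 20% | 43.2 | 78/75/72% | 49.6 | 82/80/77% |
| 33% | 36.2 | 71/69/66% | 41.5 | 76/74/71% |

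The middle figure at 54 with 10% loss is 79.6% before rounding.

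**4. Loss that still leaves 80%.** The formula needs 47/50/54 completers. From 62, that tolerates 1 − 47/62 = 24%, 1 − 50/62 = 19% and 1 − 54/62 = 13%. From 54, it tolerates 13%, 7% and 0%.

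**5. Time at risk.** Lead-in 1–2 weeks, RT 3–5 weeks, then 12 weeks: 1 + 3 + 12 = 16 to 2 + 5 + 12 = 19 weeks from first cisplatin to the scan, before the ±2-week window and any boost.

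**6. Which population do 65% and 30% describe?** Section 14.0 does not say, and the answer changes the result. Here everyone lost is taken to be a failure in the primary analysis.

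- *Whole cohort, equal loss L in both groups.* Completer rates become p/(1 − L). At 20% loss they are 81.3% v 37.5%, and power at 62 is 97/96/96%. At 33% they are 97.0% v 44.8%, and power exceeds 99% at 54 and at 62.
- *Whole cohort, unequal loss, 33% overall, f = 0.40* (0.4a + 0.6b = 0.33, where a and b are the losses in deficient and proficient patients). For a = 25%, b = 38.3%, rates are 86.7% v 48.6% and power is 90% at 62 and 86% at 54. For a = 20%, b = 41.7%, rates are 81.3% v 51.4% and power is 69% and 64%. For a = 10%, b = 48.3%, rates are 72.2% v 58.1% and power is 25% and 23%.
- *Completers only.* The primary analysis is then diluted: 0.65 × 0.67 = 43.6% v 0.30 × 0.67 = 20.1%. Primary power at 54 is 57.5/54.9/51.5%, about 52–58%.

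**The case against.** The strongest reply is that 33% progression is not 33% non-completion. The figure comes from platinum alone in an all-metastatic cohort. This trial adds RT, also takes locally recurrent disease and requires a life expectancy above 6 months. It removes patients only when progression calls for a change of treatment. A patient who progresses outside the field may finish treatment and be scanned, and cisplatin after RT is discretionary. All of this stands. A reader might infer that the protocol's own evidence contradicts the 10%, or that 80% power fails even at 62. The documents support neither: 62 patients hold 80% up to about 24/19/13% loss, and nothing shows that loss will exceed this.

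The second reply is that the rates are introduced for the primary comparison, where early progressors are failures, so they may be whole-cohort rates. Dropping those failures equally from both groups then raises completer power. That reading is open, but it does not restore the assurance. Equal 33% loss would require 97% CR in HRR-deficient completers, and unequal loss can take power well below 80%. Section 14.0 also says the rates were adjusted for the effect of RT on the target tumour, which fits a target-lesion response rate at least as well.

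Third, assay failures and non-disease leavers are replaced. This also stands. They should not be stacked on disease-related loss, and if replacements come on top of the 54, the loss in the table is the disease-related part alone.

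Finally, the plan makes no arithmetic error, and the analysis is secondary.

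**Conclusion.** The point holds as a gap in justification and an overstated assurance. The 10% has no stated basis for disease-related loss, and 80% power for the completer analysis is not secured at the accrual number now in force.

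With 65% v 30% applied to completers and 54 accrued, power is 82/80/77% at 10% loss and 71/69/66% at 33%. At 30% deficiency essentially any loss takes it below 80%. At 62, the shortfall at 33% loss is about 4 to 9 points, and there is none at 10%.

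These figures rest on two things the documents leave open: the true rate of disease-related loss, for which 10–33% is an assumed range, and the population behind the CR rates. On the whole-cohort reading, completer power could be higher or lower. On the completer reading, 33% loss would also cut primary power to about 52–58% at 54. Neither reading supports the word ensure.

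**What to change.** In Section 14.0:

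- Give a separate, justified allowance for progression, death or non-completion before the scan. State that assay failures and non-disease leavers are handled by replacement, and whether replacements are added to the 54.
- State whether 65% and 30% describe all patients with a known HRR status or completers only, and make the primary and completer power statements consistent with that choice.
- Report completer power as a range over about 10–33% loss at the actual accrual number, and reconcile 62 with 54.
- Remove the statement that 80% is ensured for the completer analysis.

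The cost is wording only, with no extra patients or procedures. The downside is that the stated power becomes less favourable.
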